12.1. Participant identification codes

Participants who provide informed consent will be assigned a participant identification (ID) code, indicating the center at which the participant was recruited and a sequential patient number. Once assigned, ID codes will not be reused for new participants. At each study center, participants will also be registered in a participant ID code list, which will link participants' ID codes to their first name, last name, e-mail address, postal address, telephone number, and Swedish Personal Identity Number. Of this information, only the participant ID

Study Name: The Fragility Fracture Trial
Version No: 2
Date: 2020-10-04
EudraCT No: 2019-004766-17

codes will be used during data collection and analysis to protect participants' integrity. Participant ID code lists will be sent encrypted to the sponsor to enable telephone interviews every 6 months of follow-up and follow-up through registries.

12.2. Electronic case report forms

The data required to be collected according to this protocol will be entered by investigators onto eCRFs, which will be pseudo-anonymized with participant ID codes. There are two exceptions to this rule, however. First, pseudo-anonymized accelerometer data will be sent to the sponsor for central wear-time validation and physical activity scoring. Second, registry-data will be collected centrally by the sponsor.

All efficacy outcomes and adverse events will be recorded using the ICD-10-SE system. Medications will be recorded using the Anatomical Therapeutic Chemical Classification System. The eCRF has not been created at the time of writing, but once this is done, its location will be specified in subsequent versions of this protocol or in the Clinical Study Report. To ensure that the system is secure, the eCRF system will be set up in collaboration with the University Hospital of Umeå Clinical Research Centre and the Department of ICT Services and System Development at Umeå University.

Investigators must ensure that eCRFs are correct and complete and that reporting takes place within the predefined time windows. An entry on the eCRF should be marked ND (Not done) if the information was not collected, NK (not known) if the information is unknown, and NA (not applicable) if the information does not apply, with appropriate Swedish translations. Any corrections made to an eCRF should be noted, signed, dated, and (if needed) explained.

12.3. Biological specimens

Samples of peripheral venous blood will be collected for analyses of serum calcium and creatinine clearance (i.e., estimated glomerular filtration rate). The total volume of blood taken from each participant will be a maximum of 20 ml (10 ml at the screening visit and 10 ml 1 week before the 24-month follow-up), unless further blood samples are needed to ensure a participant's safety. The samples will be analyzed locally at the accredited department of clinical chemistry at each study center's institution. The samples of venous blood will be destroyed immediately after analysis, but the results will be archived as source documents (see below).

Study Name: The Fragility Fracture Trial
Version No: 2
Date: 2020-10-04
EudraCT No: 2019-004766-17

12.4. Documentation

The sponsor will keep a Trial Master File and investigators will keep an Investigator Site File containing the essential documents of the trial, as defined in ICH GCP.⁵⁶ These documents will be archived in accordance with each institution's local rules, but for a minimum of 15 years.

As stated in the ICH GCP,⁵⁶ principal investigators must keep source documents, which include (but are not limited to) eCRFs, questionnaires, and laboratory reports to enable reconstruction and evaluation of the trial's results. Investigators will also keep a drug accountability log so that investigational products can be tracked and a screening log of the number of persons invited to screening and the number attending screening. The investigator must ensure that all source documents are accessible for monitoring and inspection.

12.5. Data management

The trial statistician will continuously monitor eCRFs for accuracy and completeness (including range and logical checks) and for compliance with this protocol. Any inaccuracies, inconsistencies, or deviations will be reported to the appropriate study center, with a request for a correction or an explanation. The trial database will be backed up regularly. The sponsor/coordinating investigator may also appoint staff to conduct on-site monitoring to verify eCRFs with source documents. A detailed plan for data management has not been developed at the time of writing, but it will be attached to the Clinical Study Report.

13. Statistical Analysis

Statistical analyses will be performed using the latest version of R software. All statistical hypothesis tests that can be two-sided will be two-sided. P-values <0.05 will be considered statistically significant, unless otherwise specified. P-values will be rounded to two decimal places if ≥ 0.01 and rounded to three decimal places if <0.01 but ≥ 0.001 . P-values <0.001 will be expressed as " <0.001 ".

The zoledronic acid and placebo groups will be defined according to randomization. Baseline date will be defined as the date of randomization. Follow-up time will be defined as the date of death, withdrawal, loss to follow-up, or last follow-up contact (whichever came first) minus the date of randomization plus 1 day (to account for the possibility of an event later in the day of randomization). Incomplete follow-up will be defined as follow-up time that ends before the last study contact.

Study Name: The Fragility Fracture Trial
Version No: 2
Date: 2020-10-04
EudraCT No: 2019-004766-17

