7.1. Primary outcome

Due to the high clinical relevance of most fractures, the primary outcome will be time to first new clinical fracture (ICD-10-SE codes: S12-S52, S72, S82, M48.5, M49.5, M80.0A, M80.0J, and M80.0K). Clinical fracture will be defined as any fracture that comes to medical attention, excluding fractures of the facial bones, skull, hands, and feet (ICD-10-SE codes: S02, S62, and S92), which are not generally considered osteoporotic.¹⁰ For the same reason, pathological fractures (e.g., due to cancer or osteomyelitis) will be excluded. High-energy fractures will be included because these are also associated with low bone mineral density.^{11,43}

Participants will be asked about fractures at study contacts, which will take place every 6 months of follow-up (see Section 9). Participants will also have the possibility of reporting fractures to their study center between the scheduled contacts. Participants who withdraw will be asked if they wish to answer questions about incident fractures before they formally withdraw. The Swedish Fracture Register will also be used to trace fractures for patients who consent to registry follow-up.

Fractures identified through interview will be verified through review of medical records by the study site investigator, given that the participant consents to it. Due to limited resources, the sponsor/coordinating investigator will not adjudicate fractures or other outcomes. To reduce the amount of missing data in the 10-year post-study analysis, fractures will be traced centrally by the sponsor using the above-mentioned ICD-10-SE codes in the Swedish National Patient Register. This register records all diagnoses made in inpatient care in Sweden since 1987 and all outpatient secondary (i.e., non-primary) care since 2001.⁴⁴

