7.2. Secondary outcomes

The secondary outcomes are as follows:

1. Time to first non-vertebral fracture (ICD-10-SE: S22.2, S22.3, S22.4-S22.8, S32.1-S32.5, S42, S52, S72, S82)
2. Time to first new non-hip, non-vertebral fracture (ICD-10-SE: S22.2-S22.8, S32.1-S32.5, S42, S52, S72.3-S72.4, S82)
3. Time to first hip fracture (S72.0-S72.2)
4. Time to first new forearm fracture (S52)
5. Time to first clinical vertebral fracture (S12, S22.0, S22.1, S32.0, M48.5, M49.5, M80.0A, M80.0J, and M80.0K)
6. Time to death

Study Name: The Fragility Fracture Trial
Version No: 2
Date: 2020-10-04
EudraCT No: 2019-004766-17

7. Time to first new cardiovascular event (stroke or myocardial infarction) (ICD-10-SE: I21, I60-I64)
8. Time to first new cancer diagnosis (ICD-7-SE: 140-209)
9. Occurrence of fall from standing height or less (ICD-10-SE: W00, W01, W03, W04, W18) not resulting in fracture between baseline and 48 months

Hip fractures are included among non-vertebral fractures and forearm fractures are included among non-hip, non-vertebral fractures. However, hip fractures and forearm fractures will also be assessed separately because these are common and classic types of osteoporotic fractures. Fractures, myocardial infarction, stroke, and cancer events will be identified through self-report and verified by investigators through review of medical records. Participants will also have the possibility of reporting these outcomes to their study center between the scheduled study contacts. Participants who withdraw will be asked if they wish to answer questions about these outcomes before they formally withdraw.

In the 10-year follow-up, myocardial infarction and stroke will be traced using the above-mentioned ICD-10-SE codes in the National Patient Register, SWEDEHEART, and the Swedish Stroke Register. SWEDEHEART is a register that covers most patients in Sweden who are hospitalized for acute coronary syndrome, coronary interventions, or valvular interventions.⁴⁵ The Stroke Register is a register of Swedish stroke patients, although it does not have complete coverage of the population.⁴⁶ At the 10-year follow-up, cancer events will be identified through the Swedish Cancer Register, which records all new cases of cancer in Sweden since 1958.⁴⁷ Deaths will be identified through the Swedish Cause of Death Register and by reports from family members to study centers.⁴⁸

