13.6. Efficacy analysis

All randomized patients with non-missing outcome data will be included in an efficacy analysis. For time-to-event outcomes, survival time will be calculated as date of event minus date of randomization plus 1 day (to account for the possibility of an event occurring later in the day of randomization). For participants not experiencing the event, time-to-event will be set as the follow-up time (see definition above). If the date of a participant's time-to-event outcome is incomplete, the date will be imputed as was done in a previous trial.²⁰ Thus, if the day of the month is missing, it will be imputed as the 15th. If both the day and the month are missing, these will be imputed as July 1. If the entire date is missing, the time-to-event will be set to 1 day. Events that cannot be verified through registries or medical record review will be excluded, but the number and proportion of events not verified will be reported.

For time-to-event outcomes, 4-year cumulative incidence curves will be estimated using the Kaplan-Meier method. Number of persons with an event, numbers of events, and incidence

Study Name: The Fragility Fracture Trial
Version No: 2
Date: 2020-10-04
EudraCT No: 2019-004766-17

rates (number of events/total person-years at risk of first event) will also be provided. The efficacy of zoledronic acid will be determined on the basis of the log-rank test. The relative effect of zoledronic acid versus placebo will be represented by hazard ratios (with 95% confidence intervals), estimated using Cox regression. These models will not be adjusted for covariates in the main analysis, so as to be comparable to the log rank test. The proportional-hazards assumption will be assessed using log-minus-log plots and by Wald tests of treatment-by-time product terms. In the case of a clear violation of this assumption, hazard ratios will be computed for time-intervals in which hazard ratios are more stable (e.g. 6-month or 12-month periods). As an additional analysis, the number of participants needed to treat for 4 years to prevent one fracture will be estimated for each fracture outcome using Kaplan-Meier estimated risks. Ninety-five percent confidence intervals will be provided for numbers needed to treat,^{59,60} with variance estimates derived using the method proposed by Kalbfleisch and Prentice (p. 18).⁶¹

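### The end of follow-up in Section 13 limits only participants without the event, so register fractures and deaths after loss make time at risk depend on the outcome

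*Protocol*

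**What the plan says.** The opening of Section 13 defines the end of observation: "Follow-up time will be defined as the date of death, withdrawal, loss to follow-up, or last follow-up contact (whichever came first".

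Section 13.6 then treats the two kinds of participant differently. For those with an event, "survival time will be calculated as date of event minus date of randomization plus 1 day", with no condition that the event fall within follow-up. For the rest, "For participants not experiencing the event, time-to-event will be set as the follow-up time (see definition above".

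Two outcomes in the 4-year analysis have a register source besides the interviews:
- Fracture, Section 7.1: "The Swedish Fracture Register will also be used to trace fractures for patients who consent to registry follow-up".
- Death, Section 7.2: "Deaths will be identified through the Swedish Cause of Death Register and by reports from family members to study centers".

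Section 13.6 accepts registers as verification: "Events that cannot be verified through registries or medical record review will be excluded". Section 9 lets participants opt out of register follow-up. Nothing in the protocol says whether a register event after loss counts, and nothing extends register-covered participants without an event to 48 months.

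**The concern.** Take two participants, both lost at month 12 and both covered by the Fracture Register. One has a register fracture at month 30 and contributes an event and 30 months. The other has none and contributes 12 months, although the register covered both to month 48. Time at risk has been removed only from the participant without an event.

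This is the time-at-risk rule for the primary outcome and for time to death. It feeds the log-rank test, the Cox hazard ratio, the incidence rates, and the Kaplan-Meier risks from which Section 13.6 derives the number needed to treat. Rates and risks are pushed up in both arms. If the arms lose participants at different rates, the inflation differs between arms and the hazard ratio moves with it.

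**Working it through.** **Plan's own figures.** Hazard ratio 0.65, placebo 4-year risk 10%, 90% power, two-sided 5% (Section 13.10, Appendix 1). The Schoenfeld formula gives 227 events. The treated risk is 1 − 0.90^0.65 = 0.06619. Then 227 / [(0.10 + 0.06619)/2] = 2732, and 2732/0.95 = 2876. All agree with Appendix 1; no sample-size figure is wrong.

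**Assumptions not in the documents.** Constant hazards, loss uniform over 4 years and unrelated to fracture risk, and full register capture.

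**Hazards.**
- Placebo: λ = −ln(0.90)/4 = 0.02634 per year.
- Zoledronic acid: 0.65 × 0.02634 = 0.01712 per year.

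**Rate under the literal rule.** Let p be the 4-year risk and d the proportion lost. With everyone followed to 48 months, mean time at risk is p/λ. A lost participant without an event is credited on average 2 years instead of 4, so mean time falls by 2d(1 − p):

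rate = p / [p/λ − 2d(1 − p)]

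For placebo, p/λ = 3.7965. At d = 5% the rate is 0.10/(3.7965 − 0.09) = 0.02698. At 17% it is 0.10/(3.7965 − 0.306) = 0.02865. The Kaplan-Meier column comes from simulation.

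| Loss, both arms | Placebo rate per 1000 person-years (true 26.34) | Zoledronic acid rate (true 17.12) | Placebo inflation | Kaplan-Meier placebo risk (true 10.0%) |
|---|---|---|---|---|
| 5% | 26.98 | 17.54 | +2.4% | 10.2% |
| 10% | 27.65 | 17.99 | +5% | 10.5% |
| 17% | 28.65 | 18.65 | +9% | 10.9% |

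With 70% capture the inflation is about 0.7 times as large.

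**Hazard ratio.** With equal loss the two inflations nearly cancel: 17.54/26.98 = 0.650 and 18.65/28.65 = 0.651. With unequal loss they do not. In the table, the capped column counts only events up to loss in the same simulated data.

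| Loss, placebo / zoledronic acid | Rate ratio, formula | Cox, literal rule | Cox, capped |
|---|---|---|---|
| 5% / 10% | 17.99/26.98 = 0.667 | 0.663 | 0.647 |
| 10% / 5% | 17.54/27.65 = 0.634 | 0.632 | 0.648 |

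**Type I error** (simulated log-rank test, 2900 participants): 4.5% with 5%/5% loss, 5.2% with 5%/10%, and 8.8% with an extreme 4%/17%, against 5.1% for that last split when events are capped at loss.

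**If register events after loss are ignored.** Expected events with full follow-up are 1450 × (0.10 + 0.06619) = 241. A lost participant has the event between loss and month 48 with probability p/(4λ) − (1 − p). This is 0.0491 on placebo and 0.0327 on zoledronic acid. Discarded events are 1450 × d × (0.0491 + 0.0327): about 6 at 5% loss and about 20 at 17%.

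**The case against.** **The rule is never stated outright.** Section 13 can be read as counting only events within follow-up. That reading is open, and on it there is no bias. At 5% loss it costs about 6 events and leaves 235, above the 227 required; Appendix 1 already allows for dropout. But Section 13.6 attaches the limit only to participants without the event and admits register evidence, so the literal text points the other way. The protocol fixes both halves of the rule, and they do not fit together.

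**A safeguard exists.** The second scenario of the fourth sensitivity analysis (Section 13.8) gives non-completers full event-free follow-up. If lost participants with a register fracture stay as events, this comes close to the repair. It is confined to the primary outcome, is framed as an extreme case, and also extends those who died. Time to death has no such check. Section 13.4 compares follow-up duration between arms, which would reveal unequal loss but not correct for it.

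**The size is modest.** This stands. At the planned dropout the rate error is small, and with equal loss the hazard ratio does not move.

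A reader might infer more than the documents support:
- *That the hazard ratio will be biased in favour of the drug.* Bias needs unequal loss. Post-infusion symptoms might suggest more loss on zoledronic acid, and that direction pulls the ratio toward the null. Those symptoms are described as transient, and follow-up continues after treatment stops (Section 6.1).
- *That 8% and 17% are plausible losses for the two arms.* That split gives a ratio of about 0.68, but the two figures in Section 13.10 come from different trials in different populations.
- *That myocardial infarction, stroke and cancer share the defect.* Section 7.2 ties their registers to the 10-year follow-up. Whether self-report misses fatal first events is a separate question of ascertainment, not examined here; next-of-kin interviews and serious adverse event reporting would catch some.

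**Conclusion.** The inconsistency is real and applies to fracture and death in the 4-year analysis, among participants who have not opted out of registers. On the literal reading, rates and Kaplan-Meier risks are inflated: about 2.4% at the planned 5% dropout and about 9% at 17%, the highest figure quoted in Section 13.10. The hazard ratio is safe under equal loss. It shifts by roughly 0.015 to 0.02 when one arm loses 5% and the other 10%, in a direction set by which arm loses more. On the alternative reading there is no bias, but about 6 to 20 of 241 primary events are discarded.

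These sizes rest on uniform loss, constant hazards, loss independent of fracture risk, and full capture. No size is given for death, because the documents state no mortality assumption.

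This should be fixed. The documents do not support a stronger conclusion, that the primary comparison is invalid: the effect at planned dropout is small, and one common rule brings the ratio back to about 0.65 and type I error to about 5%.

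**What to change.** State in Sections 13 and 13.6, before unblinding, one end of follow-up that applies equally to events and non-events.

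**Preferred, for fracture and death:**
- For participants who have not opted out of, or withdrawn from, register follow-up, ascertain events through 48 months in the registers already named. For fractures, use the National Patient Register as well as the Fracture Register, since Section 11 allows that Fracture Register coverage may be insufficient.
- Censor these participants at the earliest of death, emigration, withdrawal of register consent or 48 months, whether or not the last calls were answered.
- For everyone else, censor at last contact and count only events up to that date.

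**Minimum alternative:** count only events on or before the end of follow-up, for all participants. This needs one sentence and no extraction, at the price of the discarded events.

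**Cost of the preferred rule:** about two sentences, one extra extraction at 48 months (a 10-year register follow-up is already planned), and a wait for register reporting lag. Register silence would still not prove freedom from fracture, because Section 7.1 says the Patient Register does not cover primary care.

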13.1. Description of recruitment process

The recruitment process will be described in terms of the number of persons invited to a screening visit, the number who attended a screening visit, the number who provided informed consent, the number who met all eligibility criteria, and the number excluded at screening (in total and by reason for exclusion).

13.2. Baseline characteristics

All randomized participants (i.e., the intention-to-treat population) will be included in an analysis of baseline characteristics, in which the zoledronic acid and placebo groups will be compared. An analysis of baseline characteristics will also be performed for all patients who provide written informed consent but who are not randomized. Baseline values will be defined as the last measurements prior to randomization. The following numeric, binary, and multi-level categorical baseline characteristics will be analyzed:

Numeric:

1. Age, years
2. Body height, cm
3. Body weight, kg
4. Body mass index, kg/m²
5. Time since quitting smoking, years
6. Time since most recent stroke, years
7. Time since most recent myocardial infarction, years
8. Current dose of oral prednisolone, mg/day
9. Time since most recent cancer diagnosis, years
10. Number of bone fractures in adulthood (age ≥18 years)
11. Time since most recent non-hip, non-vertebral fragility fracture, months
12. Estimated glomerular filtration rate, ml/min/1.73 m²
13. Serum calcium, mmol/L
14. Hand-grip strength, kg
15. Number of steps/day
16. Time spent sedentary, hours/day
17. Time spent in light physical activity, minutes/day
18. Time spent in moderate-intensity physical activity, minutes/day
19. Time spent in vigorous-intensity physical activity, minutes/day
20. Time spent in very vigorous-intensity physical activity, minutes/day
21. Time spent in moderate- to vigorous-intensity physical activity, minutes/day
22. 10 year probability of major osteoporotic fracture according to the FRAX tool, %
23. 10 year probability of hip fracture according to the FRAX tool, %

Binary:

Study Name: The Fragility Fracture Trial
Version No: 2
Date: 2020-10-04
EudraCT No: 2019-004766-17

1. Sex (man, woman)
2. Ever undergone bone density scanning (yes, no)
3. Provided written informed consent (yes, no)
4. Ambulatory (yes, no)
5. Community dwelling (yes, no)
6. History of hip fracture (yes, no)
7. History of vertebral compression fracture (yes, no)
8. Diagnosis of osteoporosis (yes, no)
9. Remaining life expectancy <1 year (yes, no)
10. Ever use of antidepressant (yes, no)
11. Chronic obstructive pulmonary disease (yes, no)
12. History of stroke (yes, no)
13. History of myocardial infarction (yes, no)
14. Rheumatoid arthritis (yes, no)
15. Other disease that is strongly associated with osteoporosis (e.g. gluten intolerance, early menopause (before 45 years of age), chronic liver disease, or chronic gastrointestinal disease) (yes/no)
16. Use of systemic glucocorticoids at a dose of ≥ 5 mg (prednisolone or equivalent) for ≥ 3 months in the past year (yes, no)
17. Current use of oral prednisolone (yes, no)
18. Ever use of osteoporosis medication other than calcium or vitamin D (yes, no)
19. Other medication or medical condition for which bone-protective therapy is indicated (yes, no)
20. Parental history of hip fracture (yes, no)
21. Place of the most recent non-hip, non-vertebral fragility fracture (inside, outside)
22. Estimated glomerular filtration rate <35 ml/min/1.73 m² (yes, no)
23. Serum calcium <2.2 mmol/l (yes, no)

Multi-level categorical:

1. Type of fall that led to the most recent fragility fracture (ICD-10-SE codes: W00, W01, W03, W04, W18)
2. Regular cigarette smoker (current, former, never)
3. Current number of cigarettes/day (1-5, 6-10, 11-20, ≥ 21)
4. Frequency of alcohol consumption (never, ≤ 1 time/month, 1 times/week or every other week, 2-3 times/week, ≥ 4 times/week)
5. Number of glasses of alcohol on a day of drinking (1-2, 3-4, 5-6, 7-9, ≥ 10)
6. Diabetes mellitus (yes, type 1; yes, type 2; yes, but do not know type; don't know; no)
7. Cancer (current, previous, no, don't know)
8. Skeletal site of the most recent non-hip, non-vertebral fragility fracture (or the site or the most serious fracture, if multiple)
9. Method of recruitment (Swedish Fracture Registry, local hospital registry, other)
10. Study center

Study Name: The Fragility Fracture Trial
Version No: 2
Date: 2020-10-04
EudraCT No: 2019-004766-17

The accelerometer data on physical activity will be wear-time validated with activity measured in all three axes and non-wear time defined as proposed by Choi.⁵⁷ Data will only be included if the accelerometer has been worn for a least 10 hours a day for at least 4 days. Cut-points for different levels of physical activity will be selected as proposed by Freedson.⁵⁸

Numeric variables will be summarized using means, medians, standard deviations, 25th percentiles, 75th percentiles, minimums, maximums, and number and percent missing. Binary variables will be summarized as number and percent “yes” and number and percent missing. Categorical variables will be summarized as number and percent in each category and number and percent missing. Numeric values and percentages will be rounded to 1 decimal place. All variables will be summarized using number and percent of values out-of-range and, for laboratory values, number and percent outside reference values (see Section 13.7).

